5. SUBJECT ELIGIBILITY

To be eligible to participate in this study candidates must meet the following eligibility criteria during the Screening Period and must continue to meet up to prior to dosing on Study Day 1.

5.1 Inclusion Criteria

1. Must have given written informed consent (signed and dated) and any authorizations required by local law and be able to comply with all study requirements
2. Males or females aged 18 to 85 years old at the time of informed consent
 - a Females: must be non-pregnant and non-lactating and either:
 1. surgically sterile (e.g., tubal occlusion, hysterectomy, bilateral salpingectomy, bilateral oophorectomy);
 11. post-menopausal (defined as 12 months of spontaneous amenorrhea in females >55 years of age or, in females ≤ 55 years, 12 months of spontaneous amenorrhea without an alternative medical cause and FSH levels in the postmenopausal range for the laboratory involved); or,
 - iii. if engaged in sexual relations and of child-bearing potential, agree to use effective contraceptive methods (refer to [Section 6.3.1](#)) from the time of signing the informed consent form until at least 84 days (approximately 5 half-lives of ISIS 416858) after the last dose of Study Drug (ISIS 416858 or placebo).
 - b Males: Surgically sterile or if engaged in sexual relations with a female of child-bearing potential, subject is utilizing an acceptable contraceptive method (refer to [Section 6.3.1](#)) from the time of signing the informed consent form until at least 84 days (approximately 5 half-lives of ISIS 416858) after the last dose of Study Drug (ISIS 416858 or placebo).
3. End-stage renal disease maintained on outpatient hemodialysis at a healthcare center for >3 months from screening with hemodialysis at least 3 times per week for a minimum of 9 hours per week of prescribed treatment time and plan to continue this throughout the study.

5.2 Exclusion Criteria

1. Subjects with a history of a major medical event (e.g., previous acute coronary syndrome, stroke or transient ischemic attack, or systemic thromboembolic event) within 3 months of screening, major surgery within 3 months of screening, or new major physical examination finding (not accounted for by past medical history), except for documented AF.

2. Active bleeding (as judged clinically-significant by the Investigator) within the past 3 months from screening or documented bleeding diathesis (excluding uremia), coagulopathy, or recent history of prolonged compression time at arteriovenous fistula.
3. Screening laboratory results as follows:
 - Platelet count < 150,000 cells/mm³
 - < 180,000 cells/mm³ for platelet function/activation subgroup
 - INR > 1.4
 - aPTT > upper limit of normal (ULN)
 - FXI activity < 0.3 U/mL
 - ALT or AST > 2xULN
 - Total bilirubin > ULN
4. Subject is not willing to have weekly SC injections over the study period as assessed during screening.
5. Active infection requiring systemic antiviral or antimicrobial therapy that will not be completed prior to Study Day 1 (first dose) or IV antibiotic use at the time of screening.
6. Unwillingness to comply with study procedures, including follow-up, as specified by this protocol, or unwillingness to cooperate fully with the Investigator.
7. Known history of or positive test at Screening for human immunodeficiency virus (HIV), hepatitis C or chronic hepatitis B.
8. Malignancy within 5 years, except for basal or squamous cell carcinoma of the skin or carcinoma *in situ* of the cervix that has been successfully treated. Subjects with a history of other malignancies that have been treated with curative intent and which have no recurrence within 5 years may also be eligible if approved by the Sponsor Medical Monitor (or designee).
9. Treatment with another investigational drug, biological agent, or device within one month of screening, or 5 half-lives of investigational agent, whichever is longer.
10. Any history of previous treatment with an oligonucleotide (including siRNA). Subjects that have previously received only a single-dose of an ISIS-oligonucleotide as part of a clinical study may be included as long as a duration 2:4 months has elapsed since dosing.
11. Attending nephrologist answers "no" to the question, "Would you be surprised if this patient died in the next year?"
12. Within 6 months prior to screening,
 - More than 3 episodes of severe hypoglycemia requiring the assistance of another person to actively administer carbohydrate, glucagon or other resuscitative actions
 - One (1) event of hypoglycemia in which the patient required hospitalization
 - Recurrent syncope and recurrent hypotension in the inter-dialytic period requiring intervention

13. Planned major surgery in the next 6 months, including subjects receiving a kidney transplant or subjects that anticipate changing dialysis modality (i.e., hemodialysis to peritoneal dialysis).
14. Recent history of, or current drug or alcohol abuse as determined by the Investigator.
15. Concomitant use of anticoagulant/antiplatelet agents (e.g., warfarin, dabigatran, rivaroxaban, clopidogrel) that may affect coagulation (except low dose aspirin (≤ 100 mg/day) during Treatment and Post-treatment Evaluation Periods is not allowed. Stable doses of heparins during dialysis are permitted.
16. Uncontrolled hypertension as judged by the Investigator. For example, patients with a pre- or post-dialysis blood pressure (BP) that is > 180 mmHg on at least 3 of the last 5 dialysis treatments.
17. Have any other conditions, which, in the opinion of the Investigator or Sponsor would make the subject unsuitable for inclusion, or could interfere with the subject participating in or completing the study.

6. STUDY PROCEDURES

6.1 Study Schedule

The study period for an individual patient consists of a 4-week Screening Period for procedures followed by a 26-week Treatment Period, and a 12-week Post-Treatment Evaluation Period. Additional outpatient visits may be scheduled if required for further evaluation of an abnormal laboratory value or reported AE.

For patients participating in the PK substudy, there are 4 additional visits than those in the main study, occurring on Study Days 2, 177, 178, and 183. On Study Day 1 and at the end of the treatment period on Study Day 176, PK blood sampling is required at 1, 2, 3, 4, 6, and 10 hours after Study Drug administration. Two (2) of the 4 additional visits may be on non-dialysis days (Study Days 2 and 177).

For patients participating in the platelet subgroup, no additional visits are required. Any AEs, concomitant medications, and other safety and tolerability profiling data will be promptly reported and reviewed by Sponsor's Medical Monitor (or designee).

All required study procedures are outlined in [Appendices A, B, and C](#).

6.1.1 Screening

Day -49 to Day -14: Written informed consent for the study will be obtained prior to the performance of any study-related procedures.

Day-28 to Day-I: A 4-week period is provided to complete Screening assessments and procedures and to determine subject eligibility for the study. Subjects will be questioned for medical history, and undergo physical examination, confirmation of their ESRD status, 12-lead electrocardiogram (ECG), vital signs, body weight, and height. Race and ethnicity data will be collected as part of the demographic information for all screened subjects during the screening period.

Subjects will also be screened for infections of HIV, Hepatitis B and C, and for blood coagulation abnormalities including prolonged aPTT, PT, and international normalized ratio (INR), and low FXI activity levels(< 0.3 U/mL). All women will have a serum pregnancy test done between S-28 and S-14 that must be resulted prior to dosing on Study Day 1. Follicle-stimulating hormone (FSH) will be measured to confirm menopause in women< 55 years of age that have 12 months of spontaneous amenorrhea without an alternative medical cause. Additional blood samples will be taken for routine clinical laboratory testing ([Appendix A](#)).

In order to reduce the burden of unnecessary procedures on subjects who subsequently elect not to participate in the study or continue with study procedures, all subjects will confirm tolerance of SC administration prior to randomization. This injection will follow the same procedures as injections of the Study Drug (ISIS 416858 or placebo) during the treatment period. Specifically, during the screening period on Study Days S-14 (\pm 3) and S-7 (\pm 3), subjects should receive 2 noncontiguous SC injections of 0.75 mL saline within 2 hours after dialysis as described in [Section 3.4.1](#).

The Screening results will be made available to decide individual subject's eligibility against inclusion/exclusion criteria ([Section 5.1](#) and [5.2](#)). Individual subjects will be disqualified if results of any laboratory test are clinically-significant as judged by the Investigator or Sponsor's Medical Monitor (or designee). Eligible subjects will be enrolled into the study.

6.1.2 *Baseline (Day 1)*

Baseline for the routine clinical assessments of chemistry and hematology, PD markers, assessment of clotting, PK assessments, vital signs and ECG for the study will be the time-point prior to the first administration of Study Drug and prior to dialysis on Day 1 ([Appendix A](#)). If Day 1 values are not available, screening values will be used. For Urea Reduction Ratio, the blood collections for blood urea nitrogen (BUN) prior to dialysis as well as the post-dialysis sample on Day 1 will be used.

6.1.3 *Treatment Period (Day 1 to Day 176)*

Enrolled subjects may be administered ISIS 416858 or placebo immediately after dialysis is completed (when blood is returning to the subject) but must be within 2 hours (preferably within 15 minutes) approximately once each week for a total of 26 weeks of treatment.

Once-weekly SC administration will occur during Weeks 1 to 26 (Days 1, 8, 15, 22, 29, 36, 43, 50, 57, 64, 71, 78, 85, 92, 99, 106, 113, 120, 127, 134, 141, 148, 155, 162, 169, and 176).

For Study Drug administration on Study Day 1, no dosing window is allowed. For Weeks 2 to 26, a \pm 3-day window may be utilized but Study Drug should be administered each week. Study Drug doses should be administered at least 72 hours apart.

Additionally, no dose of Study Drug will be administered before reviewing a valid platelet result. Valid platelet counts must be conducted every 2 weeks and reviewed prior to dosing. If the platelet result is unavailable (e.g., due to hemolysis, clumping, etc.) from the central lab, a repeat local lab will be conducted and reviewed prior to dosing.

Any questions on study procedures and visit windows may be directed to the Sponsor (or designee).

During all subject contacts, Investigators will check for and record:

- Bleeding events
- AEs
- Concomitant medication changes

Safety and clinical laboratory evaluations as well as PD markers, assessment of clotting, blood sampling, including those for routine PK as well as PK substudy analysis will be performed as indicated in [Appendices A, B, and C](#). Subjects participating in the platelet substudy will have additional blood sampling and processing on Study Days 1, 78, and 176 during the Treatment Period.

Any AEs, including bleeding events, will be recorded. This may include additional information regarding events of interest (i.e., thrombotic events).

6.1.4 Post-Treatment Evaluation Period

After completing the 26 weeks of the Treatment Period, subjects will return for follow-up visits as indicated in Appendix A. Patients will be followed until the Study Center visit on Day 260. During the Post-Treatment Evaluation Period, a visit window of \pm 3 days is allowed for Days 183, 190, and a visit window of \pm 7 days is allowed for visits between Days 204 and 260.

For all cohorts, at all subject contacts, Investigators and staff will check for and record:

- Bleeding events
- AEs
- All concomitant medication changes

Safety and clinical laboratory evaluations as well as PD markers, assessment of clotting, blood sampling, including those for routine PK as well as PK substudy analysis, will be performed as indicated in Appendices A, B, and C. Subjects participating in the platelet substudy will have additional blood sampling and processing on Study Day 260, the last day of the Post-Treatment Evaluation Period.

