2 ANALYTICAL PLAN

2.1 General Overview of Analyses

2.1.1 General Statistical Methods

Descriptive summary statistics including number of patients, mean, standard deviation, median, and range (minimum, maximum) for continuous variables, and counts and percentages for categorical variables will be used to summarize most data. All statistical tests will be conducted using 2-sided tests with 5% Type I error rate unless otherwise stated.

PK parameters will be summarized using number of patients, mean, standard deviation, coefficient of variation (CV), geometric mean, median, minimum, and maximum.

All analyses and tabulations will be performed using SAS® Version 9.2 or higher and Phoenix/WinNonlin version 6.1 or higher on a PC platform.

A separate analysis for on-treatment period might be provided if deemed necessary.

Pooled groups:

Patients who are placebo-treated will be pooled and analyzed as a single placebo group.

Patients who are ISIS 416858-treated may be pooled and summarized as the ISIS 416858 total group.

Baseline definition:

Unless otherwise specified, baseline for all safety laboratory results will be defined as the last non-missing measurement prior to the first dose. For post-dialysis Blood Urea Nitrogen (BUN) measures for Urea Reduction Ratio (URR) determination, post-dialysis baseline will be defined as the last non-missing post-dialysis measurement prior to the first dose

Analytical visits:

All post-baseline data will be summarized according to the visit windows in the table below. For patients who have multiple visits within a window, the average will be used in the summary for continuous variable and the worst case result will be used for categorical variable.

Table I Visit window for Clotting

Analysis visit	Visit window
Screening	<1
Baseline	last non-missing measurement prior to the first dose
Day8	[2, 11]
Day 15	[12, 21]
Day29	(22, 35]
Day43	[36, 49]
Day 57	[50, 63]
Day71	[64, 77]
Day 85	[78, 91]
Day99	(92, 105]

Day 113	[106, 116)
Day 120	[117, 126)
Day 134	(127, 140)
Day 148	(141, 154)
Day 162	[155, 168)
Day 176	[169, 182]
Day 190	(183, 196]
Day 204	[197, 210]
Day 218	[211, 224]
Day 232	[225, 238]
Day 246	(239, 252]
Day 260	[253, 266]

Table 2 Visit window for Vital Signs

Analysis visit	Visit window
Baseline	last non-missing measurement prior to the first dose
Day 5	(2, 6)
Day 8	[7, 9]
Day 12	[10, 13]
Day 15	[14, 17]
Day 22	[18, 25)
Day 29	[26, 32)
Day 36	[33, 39)
Day 43	[40, 46]
Day 50	[47, 53]
Day 57	[54, 60]

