Hct	hematocrit
HCV	hepatitis C virus
HIV	human immunodeficiency virus
HR	heart rate
ICH	International Conference on Harmonization
IEC	Independent Ethics Committee
INR	international normalized ratio
IRB	Institutional Review Board
ISIS 416858	antisense inhibitor of Factor XI
IV	intravenous(ly)
IXRS	automated randomization system
kg	kilogram
MB	major bleeding
MCH	mean corpuscular hemoglobin
MCHC	mean corpuscular hemoglobin concentration
MCV	mean corpuscular volume
MedDRA™	Medical Dictionary for Regulatory Activities
mg	milligram
MI	myocardial infarction
mL	milliliter
MPV	mean platelet volume
mRNA	messenger ribonucleic acid
NCS	not clinically-significant

NT-proBNP	N-terminal pro-brain natriuretic peptide
PD	pharmacodynamic(s)
PK	pharmacokinetic(s)
PT	prothrombin time
RNase H1	ribonuclease H1 (a non-specific endonuclease that catalyzes the cleavage of RNA via a hydrolytic mechanism)
SAE	serious adverse event
SAP	Statistical Analysis Plan
siRNA	small interfering ribonucleic acid
SC	subcutaneous(ly)
Study Day 1	defined as the first day Study Drug is administered to the subject
Study Drug	ISIS 416858 or placebo
SUSAR	suspected unexpected serious adverse reaction
Tmax	time to maximal concentration
ULN	upper limit of normal
VTE	venous thromboembolism
WBC	white blood cell
WHO	World Health Organization
W,wk	week
WMA	World Medical Association

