3.4 Overall Study Duration and Follow-up

For all cohorts, the Study will consist of a 4-week screening period for procedures after the informed consent is signed. An additional 21 days is permitted prior to screening period for signing of the informed consent. All cohorts will consist of a 26-week Treatment Period, and a 12-week Post-Treatment Evaluation Period. For all cohorts, please refer to the Schedule of Procedures in [Appendix A](#).

Subjects may be required to attend additional visits for monitoring of adverse events (AE) or abnormal investigation results. The frequency of additional monitoring will be determined by the Investigator in consultation with the Sponsor.

If Study Drug is discontinued for any reason, subjects are encouraged to continue their regular assessments for the duration of the treatment period and post-treatment evaluation period, unless subject informed consent is withdrawn.

3.4.1 *Screening*

After signing the informed consent form, subject eligibility for the study will be determined within 4 weeks prior to Study Day 1.

During the screening period, at Study Days S-14 (\pm 3) and S-7 (\pm 3), subjects should receive 2 noncontiguous SC injections of 0.75 mL saline. As with Study Drug, these may be administered immediately after dialysis is completed when blood is returning to the subject but must be within 2 hours after dialysis (within 15 minutes is preferred) to determine tolerability to SC injections.

All women will have a serum pregnancy test done between Study Days S-28 and S-14 that must be resulted prior to dosing on Study Day 1.

All screening lab re-tests should be resulted by the central lab prior to randomization on Study Day 1.

3.4.2 *Treatment*

Eligible subjects will receive study treatment every week for 26 weeks. The treatment period consists of the period from the first Study Drug (ISIS 416858 or placebo) injection to the last injection on Day 176 (Week 26), or early study termination.

3.4.3 *Post-Treatment*

Subjects will have follow-up evaluation visits on Study Week 27 (PK Subgroup only), and for Study Weeks 28, 30, 32, 34, 36, 38 (all subjects), or early study termination. The final study visit will be Study Day 260.

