10.2 Sample Size Considerations

The sample size was selected based on prior experience to ensure that the safety, tolerability and PK/PD relationships will be adequately assessed while minimizing unnecessary patient exposure. There is no statistical rationale for the selected sample size.

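### A final visit on Day 267 is within the protocol, but the SAP's Day 260 windows for clotting, vital signs and chemistry/hematology/coagulation end at Day 266 and leave it out of the by-visit summaries

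*Combined protocol and SAP*

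**What the plan says.** Protocol Section 3.4.3 fixes the end of follow-up: "The final study visit will be Study Day 260". Section 6.1.4 gives a window of ±7 "days is allowed for visits between Days 204 and 260", and the Appendix A schedule shows ±7 for the late follow-up columns. Days are counted from Study Day 1, which the protocol glossary gives as "defined as the first day Study Drug is administered to the subject".

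SAP Section 2.1.1, under analytical visits, states: "All post-baseline data will be summarized according to the visit windows in the table below". Six window tables follow. For Day 260 they give:

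- Days 253 to 266 in Table 1 (clotting), Table 2 (vital signs) and Table 4 (chemistry, hematology and coagulation panel, which includes FXI and aPTT);
- Days 218 to 273 in Table 3 (ECG);
- Days 246 to 273 in Table 5 (BUN and URR) and Table 6 (inflammatory markers).

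Section 2.1.1 has no rule for a value that falls outside every window. SAP Section 2.1.5 says that missing values are in general not imputed.

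**The concern.** The protocol and the SAP disagree by one day about what counts as the final visit, and the SAP also disagrees with itself. For a subject seen on Day 267, the ECG, urea and inflammatory results are reported at Day 260. The platelet count, FXI, aPTT, clotting score and vital signs taken at the same attendance are reported at no visit.

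The uncovered day is one on which a visit could plausibly fall. Study assessments are tied to dialysis sessions, and Day 267 is the same weekday as Day 260. A subject who misses the final visit and is seen at the same weekly session one week later lands on it.

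Day 260 is the last scheduled look at recovery after dosing, 84 days after the last planned dose on Day 176 (260 − 176 = 84). What is at stake is the completeness of that last row of the by-visit tables and of any treatment comparison made there.

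**Working it through.** **Inputs.** Final visit Day 260 (protocol 3.4.3); permitted deviation ±7 days (protocol 6.1.4, Appendix A); SAP windows (Section 2.1.1, Tables 1 to 6). No power or sample-size quantity enters.

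**Step 1: permitted range.** 260 − 7 = 253 and 260 + 7 = 267, which is 267 − 253 + 1 = 15 days.

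**Step 2: reproduce the SAP's figure.** In Tables 1, 2 and 4 the follow-up visits are 14 days apart, and each window runs from target − 7 to target + 6, so that neighbours adjoin without overlap. For Day 260 this gives 260 − 7 = 253 and 260 + 6 = 266, exactly the SAP's limits. The 266 is the tiling rule carried through to the last visit.

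**Step 3: compare the two at each late follow-up visit.**

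| Target | Permitted by protocol | Window in Tables 1, 2, 4 | Permitted day outside window | Where that day goes |
|---|---|---|---|---|
| 204 | 197–211 | 197–210 | 211 | Day 218 |
| 218 | 211–225 | 211–224 | 225 | Day 232 |
| 232 | 225–239 | 225–238 | 239 | Day 246 |
| 246 | 239–253 | 239–252 | 253 | Day 260 |
| 260 | 253–267 | 253–266 | 267 | none |

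The +7 day is outside the window at all five visits. At the first four the next window catches it, so the value is reported one visit late. At Day 260 there is no next window.

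**Step 4: the other tables.** 267 ≤ 273, so Tables 3, 5 and 6 all cover Day 267. In Tables 5 and 6 the limit is 260 + 13 = 273, which fits their wider 28-day tiling (target − 14 to target + 13).

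**Step 5: weekday.** (260 − 1) mod 7 = 0 and (267 − 1) mod 7 = 0. Days 260 and 267 both fall on the weekday of Day 1.

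**Step 6: which analyses use the Day 260 row.** Exposed are the by-visit summaries of chemistry and hematology (SAP 2.3.4), vital signs (2.3.5), FXI and aPTT with their comparisons against pooled placebo (2.4), and clotting category by visit (2.4). Not exposed are:

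- the primary outcome, which is major plus clinically relevant non-major bleeding during the treatment period;
- the clotting category 3 or greater analysis, which is cut off at last dose + 7 days;
- the ordinal clotting analysis at Week 26 or early termination;
- average FXI activity over Days 50 to 176.

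**The case against.** The strongest reply is that this is one day at one descriptive follow-up visit, and that 266 is the product of a consistent tiling rule rather than a slip. Both halves are fair. The rule does its job at Days 204 to 246, where a later limit would overlap the next window. That reason does not apply at Day 260: no window follows, so stopping at +6 prevents no overlap and only excludes a compliant day.

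A reader might infer more than the documents support, in three ways.

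- **That the data are deleted.** The SAP has no deletion rule. A Day 267 value is simply assigned to no analysis visit. It stays in the database, individual FXI and aPTT results are still listed (SAP 2.4), and the confirmed ALT/AST categories are tabulated with no visit-window restriction (SAP 2.3.4).
- **That a sizeable share of final visits is affected.** On a three-times-weekly schedule one can count dialysis days at −7, −5, −3, 0, +2, +4 and +7 and arrive at 1 in 7, or at 1 in 3 if only −7, 0 and +7 are allowed. These are counts of calendar slots and would be loss rates only if visits were spread evenly over the slots. Nothing in the documents says so. Nor does anything hold subjects to one weekday, and a subject who misses Day 260 can be seen at +2 or +4, both inside the window.
- **That all laboratory windows are short.** Only Table 4 is. BUN/URR and inflammatory markers are covered.

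**Conclusion.** The mismatch is real and the SAP is wrong as written on this point, with small impact. Of the 15 permitted days for the final visit, Tables 1, 2 and 4 cover 14. The day left over, Day 267, maps to no analysis visit, while Tables 3, 5 and 6 count the same attendance as Day 260. The consequence is confined to the Day 260 row of the by-visit summaries for clotting, vital signs and the Table 4 laboratory panels, and to the FXI and aPTT comparisons at that visit. How many subjects would be affected is not given and could be close to zero.

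This rests on three readings: that the ±7-day range includes Day 260 itself, as Appendix A supports; that the FXI and aPTT comparisons are made visit by visit, as their summaries are; and that the windows are applied as stated, with no unwritten rule returning a stray value to its nominal visit. Some brackets in the window tables are garbled in the text available, but the Day 260 entries in Tables 1, 2 and 4 agree.

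**What to change.** In SAP Tables 1, 2 and 4, change the Day 260 window from [253, 266] to [253, 267]. That is the smallest change that covers every permitted day, and it overlaps nothing because no later window exists.

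An upper limit of 273 would also work and would match the upper limit (though not the lower one) of Tables 3, 5 and 6. It would, however, admit Days 268 to 273, which are outside the protocol's visit window, so choosing it should be a deliberate decision.

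The cost is three table cells, with no protocol amendment and no new data. It is best done before unblinding, so that no Day 267 visit needs a case-by-case decision.
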